## 6 TRIAL METHODS

#### 6.1 Assessment of efficacy

Efficacy variables:

- Survival / date of death requiring a death certificate
- ALSFRS-R
- SEIQoL
- sVC

The Efficacy variables listed above will be determined at the study site using standard methods.

## 6.2 Assessment of safety

#### 6.2.1 Safety Variables

- Blood cell count (RBC, WBC, Hb, Hct, MCV, MCH, MCHC, PLT)
- ASAT
- ALAT
- CK
- Creatinine
- Blood glucose
- Beta-HCG

#### 6.2.2 Adverse events

#### 6.2.2.1 Definitions

### Adverse Event (AE)

According to GCP, an adverse event (AE) is defined as any untoward medical occurrence in a patient treated with a pharmaceutical product and which does not necessarily have a causal relationship with this treatment. An AE can therefore be any unfavorable and unintended sign (including an abnormal laboratory finding), symptom, or disease temporally associated with the use of a medicinal investigational product, whether or not related to that product.

An AE may be:

- a new symptom or medical condition
- a new diagnosis
- a change in laboratory parameters
- an intercurrent illness or accident
- worsening of a medical condition/diseases existing before the start of the clinical trial
- recurrence of a disease
- an increase in frequency or intensity of episodic diseases.

This definition also applies to events occurring in any comparative group (active treatment or placebo) or during the placebo-treatment phase or during periods when the patient is not receiving any study medication.

Surgical procedures themselves are not AEs; they are therapeutic measures for conditions that require surgery. The condition for which the surgery is required may be an AE. Planned surgical measures permitted by the clinical trial protocol and the condition(s) leading to these measures are not AEs, if the condition leading to the measure was present before inclusion in the trial. In the latter case the condition should be reported as medical history.

Change in laboratory parameters: The criteria for determining whether an abnormal test finding should be reported as an adverse event are as follows:

- Test result is associated with accompanying symptoms, and/or
- Test result requires additional diagnostic testing or medical/surgical intervention, and/or
- Test result leads to a change in trial dosing outside of protocol-stipulated dose adjustments, or discontinuation from the trial, significant additional concomitant drug treatment, or other therapy, and/or
- Test result is considered to be an adverse event by the investigator or sponsor.

### Serious adverse event (SAE)

A serious adverse event (SAE) is one that at any dose (including overdose):

- results in death
- is life-threatening
- requires patient hospitalization or prolongation of existing hospitalization
- results in persistent or significant disability/incapacity or
- is a congenital anomaly/birth defect
- is an important medical event.

"Life-threatening" means that the patient was at immediate risk of death at the time of the serious adverse event; it does not refer to a serious adverse event that hypothetically might have caused death if it were more severe.

If the admission is pre-planned (i.e., elective or scheduled surgery arranged prior to start of the trial) or not associated with an adverse event (e.g., social hospitalization for purpose) or results in a hospital stay less than 12 hours, the serious criterion "hospitalization" is not fulfilled. However, it should be noted that invasive treatment during a hospitalization may fulfill the criteria of "medically important" and may be reportable as a serious adverse event dependent on clinical judgment.

"Persistent or significant disability or incapacity" means that there is a substantial disruption of a person's ability to carry out normal life functions. The irreversible injury of an organ function (e.g., paresis, diabetes, cardiac arrhythmia) fulfills this criterion.

Medical and scientific judgment should be exercised in deciding whether expedited reporting is appropriate in situations where none of the outcomes listed above occurred. Important medical events that may not be immediately life-threatening or result in death or hospitalization but may jeopardize the patient or may require intervention to prevent one of the other outcomes listed in the definition above should also usually be considered serious. Examples of such events include allergic bronchospasm requiring intensive treatment in an emergency room or at home, convulsions that do not result in patient hospitalization, or the development of drug dependency or drug abuse. A diagnosis of cancer during the course of a treatment should be considered as medically important.

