# 1 INTRODUCTION

## 1.1 Scientific background

Amyotrophic lateral sclerosis (ALS) is a severe neurodegenerative disease characterized by progressive degeneration of the anterior horn cells of the spinal cord, their homologues in the brain stem and the upper motor neurons in the primary motor cortex. Clinically, the disease progresses from initial asymmetric weakness, wasting and atrophy to complete loss of spinal and bulbar motor functions. The upper motor neuron component is clinically mirrored by hyperactive tendon jerks, pseudobulbar emotional lability, and less frequently spasticity.

The ALS Research Committee of the World Federation of Neurology has established research diagnostic guidelines, the El Escorial criteria [1, 2] (http://www.wfnals.org). ALS is considered an orphan disease: its incidence is estimated with 1.5 –3 /100000/year and prevalence rates are 3-6/100000 [3]. Treatment of ALS remains unsatisfactory; riluzole, a benzothiazole derivative and glutamate release blocker, has been approved for use in ALS because of its modest effect on survival [4]. The drug is generally well tolerated by the patients although liver toxicity must be controlled (http://www.cochrane.org).

Based on a rare cause of the disease, mutations in the gene for the cytosolic form of the copper/zinc superoxide dismutase (Cu/Zn SOD), a transgenic animal model has been developed. This G93A model of fALS has led to the discovery of several experimental drugs; in particular, a dose-dependent effect of rasagiline on survival (alone and in combination with riluzole) has been demonstrated in a mouse carrying a low copy number of the human disease-causing gene [5].

Rasagiline [N-propargyl-(1R)-aminoindan] is a selective irreversible second-generation monoaminooxidase (MAO)-B inhibitor with symptomatic efficacy in Parkinson's disease (PD) with a favourable tolerability profile [6]. Preclinical studies have demonstrated that rasagiline has neuroprotective effects both in in vitro and in vivo models, suggested to be related to its propargyl moiety rather than MAO inhibition. Structure activity studies have established that N-propargylamine is essential for the neuronal cell survival activity of rasagiline since this moiety itself revealed similar protective effects and mechanisms of actions [5]

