6.2.2.5 Immediate reporting of SAEs by investigator

SAEs must immediately (within 24 hours of the investigator's awareness) be reported to:

[name]. [name], MD Department of Neurology University of Ulm, Germany [contact] [contact]

Both the investigator and the sponsors safety contact will adhere to the requirements of the German GCP-Ordinance (§§12, 13) on documentation and notification.

The initial SAE Report should be as complete as possible including the essential details of patient's identification (screening number, random number), the serious adverse event (medical term, diagnosis), the trial medication and the assessment of the causal relationship between the event and the trial medication. The SAE report must be reviewed and signed by the investigator.

The investigator should provide related additional information on the clinical course and the outcome of each SAE as soon as possible (Follow up report).

The "Serious Adverse Event Form" is provided in the Investigator Site File.

The investigator should also inform the trial monitor in all cases.

The following are not considered to be serious adverse events:

- An event causing a brief visit to a hospital consultation, an open-door or day hospital,
- outpatient treatment in the emergency department although the reason for which this treatment was instituted may be serious, or
- admission to hospital (more than one night in a hospital bed) including surgical operations planned before or during the study if the condition was present before the study and provided that it does not worsen during the study.

The following are considered to be serious adverse events even if they do not comply with the definition:

- Adverse events caused by misuse or overdose,
- Any pregnancy discovered during the study.

Note: a state of pregnancy is an exclusion criterion. Hence contraceptive measures are necessary in women with childbearing potential throughout the study. However if pregnancy is discovered during the study the trial treatment must immediately be discontinued and the pregnancy followed to term.

Worsening of a sign or symptom of the condition under treatment will normally be measured by efficacy parameters. However, if the outcome fulfills the definition of "serious adverse event", it must be reported as such.

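### Naming paresis in the SAE disability criterion, together with the override in Section 6.2.2.5, leaves it contradictory whether non-fatal ALS progression is an SAE

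*Protocol*

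**What the plan says.** Four parts of the protocol bear on whether non-fatal ALS progression is a serious adverse event.

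- **Section 6.2.2.1, adverse event definition.** An adverse event may be "worsening of a medical condition/diseases existing before the start of the clinical trial".
- **Section 6.2.2.1, SAE definition, footnote 3.** Persistent or significant disability "means that there is a substantial disruption of a person's ability to carry out normal life functions". The next sentence adds: "The irreversible injury of an organ function (e.g., paresis, diabetes, cardiac arrhythmia) fulfills this criterion".
- **Section 6.2.2.4.** At each visit after screening, the suggested question asks about symptoms other than those belonging to the illness. The same section requires events detected by the investigator to be documented as well.
- **Section 6.2.2.5.** SAEs go to the sponsor's safety contact within 24 hours of awareness. On the study disease, the default is: "Worsening of a sign or symptom of the condition under treatment will normally be measured by efficacy parameters". The following sentence says that if the outcome meets the SAE definition, "it must be reported as such".

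Section 1.1 describes the disease itself: "the disease progresses from initial asymmetric weakness, wasting and atrophy to complete loss of spinal and bulbar motor functions". The only disease-specific reporting exemption is in Section 6.2.2.7. It concerns deaths, and covers systematic unblinding and expedited reporting.

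**The concern.** Footnote 3 reads as general-purpose text. In most trials irreversible paresis would be a sensible example of a serious outcome. In ALS it is what the disease does. Because the footnote says such injury fulfils the criterion, the override in Section 6.2.2.5 reaches the very events that the preceding sentence leaves to the efficacy measures.

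What is at stake is how informative the safety data are. About 15 sites must apply text that points both ways. A site that follows the footnote literally will file progression as SAEs; a site that follows the efficacy default will not. The SAE counts then partly reflect site habit and disease course. The DSMB, which reviews safety data every three months, sees the same mixture.

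**Working it through.** The protocol states no expected SAE rate, so there is no figure to reproduce. The main check is to read the passages together; a calculation then illustrates the scale.

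**1. Literal chain**

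- Section 1.1: progressive loss of motor function is the expected course.
- Section 6.2.2.1: worsening of a pre-existing disease can be an adverse event.
- Footnote 3: irreversible paresis meets the disability criterion, so the event is serious.
- Section 6.2.2.5, override: a worsening that meets the SAE definition is reported as an SAE, within 24 hours.

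**2. Text pointing the other way**

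- Footnote 3 opens with a threshold of substantial disruption, which a small increment of weakness need not reach.
- Section 6.2.2.5 makes the efficacy measures the normal place for worsening.
- Section 6.2.2.4 steers the patient's answer away from illness-related symptoms, although investigator-detected events are still recorded.

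**3. Is there an exemption elsewhere?** The list of non-SAEs in Section 6.2.2.5 covers brief hospital visits, outpatient emergency treatment and certain planned admissions. Section 6.2.2.7 covers deaths. Neither covers non-fatal progression, so the conflict is not resolved in the protocol.

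**4. Scale against deaths.** Inputs are 125 patients per arm (Section 3.2) and 18-month survival of 70% and 85% (Section 7.1). Planned deaths by 18 months, ignoring dropout, are 125 × 0.30 + 125 × 0.15 = 37.5 + 18.75 = 56.25. If a share q of the 250 patients had at least one progression SAE (an assumption), the number of such patients would be:

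| q | Patients (250 × q) | Per planned death |
|---|---|---|
| 10% | 25 | 0.4 |
| 25% | 62.5 | 1.1 |
| 50% | 125 | 2.2 |
| 90% | 225 | 4.0 |

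The documents do not say where q would lie.

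**5. Illustration of dilution.** Assume non-progression SAE rates p of 20% and 35%, 125 per arm, and progression SAEs independent of arm and of other SAEs. The proportion with any SAE is 1 − (1 − p)(1 − q). For q = 50% this gives 1 − 0.80 × 0.50 = 60% and 1 − 0.65 × 0.50 = 67.5%. Power is for an uncorrected two-sided 5% chi-square test on any SAE, by exact binomial enumeration:

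| q | Any-SAE rates | Difference (points) | Power |
|---|---|---|---|
| 0% | 20.0% vs 35.0% | 15.0 | 76% |
| 10% | 28.0% vs 41.5% | 13.5 | 62% |
| 25% | 40.0% vs 51.25% | 11.25 | 43% |
| 50% | 60.0% vs 67.5% | 7.5 | 24% |
| 80% | 84.0% vs 87.0% | 3.0 | 10% |
| 90% | 92.0% vs 93.5% | 1.5 | 7% |

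Every p and q here is assumed. The table applies only to a pooled any-SAE comparison, which the protocol does not define; the synopsis says only that chi-square tests compare adverse event frequencies.

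**The case against.** The strongest reply is that the text can be read so that nothing is wrong. Paresis is an example under a heading that requires substantial disruption, so not every loss of strength is serious. If the override took in all progression, the word normally in Section 6.2.2.5 would have no effect. A narrower reading, in which the override catches deaths, life-threatening events, admissions and marked new incapacity, gives both sentences work to do. Patients also enter with established weakness, which is not a new event. This shows that the literal reading is not the only one. It does not remove the conflict: the second sentence of footnote 3 is categorical, and the protocol never tells sites which reading to use.

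A reader might go further and infer that nearly every patient will have a progression SAE and that genuine serious events will be swamped. The documents do not support this. They give no rate, and the threshold, the default and the visit question all work against it. Section 7.4 also tabulates events by body system and preferred term, with subcategories by intensity and relationship, and lists every event, so progression reports could largely be told apart.

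The burden is also limited. The 24-hour duty runs from the investigator to the sponsor's safety contact, and progression judged unrelated is not a SUSAR. Section 6.2.2.7 leaves SAE workflow to a separate document, such as a safety manual, which is not shown and might draw the line. These points stand and limit the size of the problem. Such a document would still have to work around a definition that the protocol itself fixes.

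Finally, broad capture can be defended as the conservative choice. That is fair, but the default in Section 6.2.2.5 shows that the protocol did not intend it for ordinary worsening.

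**Conclusion.** The point holds as an internal conflict in the safety definitions. Footnote 3 and the override in Section 6.2.2.5, read literally, make non-fatal ALS progression a 24-hour SAE; the default in Section 6.2.2.5 and the question in Section 6.2.2.4 point the other way. The likely results are site-dependent SAE reporting and some dilution of SAE counts and DSMB data.

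The size cannot be derived from the protocol. The power figures above show direction only, on assumed rates and for a pooled test that is not specified. Time to death, the sample size and expedited SUSAR reporting are not touched. This is an inexpensive improvement that should be made; it does not threaten the trial's main conclusion.

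**What to change.** Reconcile Sections 6.2.2.1, 6.2.2.4 and 6.2.2.5 by a short amendment, repeated in the safety manual:

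- In footnote 3, remove paresis from the examples.
- Add to footnote 3, for instance: *Loss of motor, bulbar or respiratory function consistent with the expected course of ALS is captured by ALSFRS-R and sVC and does not by itself meet the disability criterion. It remains an SAE if it is fatal, life-threatening, leads to hospitalization, or is judged by the investigator to be atypical or possibly drug-related.*
- Point the closing paragraph of Section 6.2.2.5 to that text, and check that the question in Section 6.2.2.4 is consistent with it.

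The work is a few sentences, and sites would probably file fewer SAE forms. The real cost is that a drug effect speeding up weakness in a way that looks typical would no longer appear in SAE counts. It would show only in the ALSFRS-R and sVC comparisons, which Section 7.3.2 analyses without replacing missing values, so that fallback is imperfect.

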#### Clarification of the difference in meaning between "serious" and "severe":

The terms "serious" and "severe" are not synonymous but are often used interchangeably. The term 'severe' is often used to describe the intensity (severity) of a specific event; the event itself, however, may be of relatively minor significance (such as severe headache). This is not the same as "serious", which is based on patient/event outcome or action criteria usually associated with events that pose a threat to a patient's life or functioning. Seriousness (not severity) serves as a guide for defining regulatory reporting obligations."

#### Adverse Reaction (AR)

An adverse reaction is any noxious and unintended response to an investigational medicinal product (the causal relationship between the medicinal product and the adverse event is at least a reasonable possibility).

#### Serious Adverse Reaction (SAR)

If there is a causal relationship between a serious adverse event and trial medication then the event is called serious adverse reaction (SAR).

#### Suspected Unexpected Serious Adverse Reaction (SUSAR)

A SUSAR is a serious adverse reaction which is unexpected.

An unexpected serious adverse reaction is any adverse reaction, the nature or severity of which is not consistent with the applicable product information (i.e., the Investigator's Brochure or the current SmPC).

### 6.2.2.2 Assessment of AEs by investigator

Patients must be carefully monitored for adverse events by the investigator. The intensity of the adverse events and the causal relation to trial medication and/or procedures are to be assessed.

#### Intensity/Severity

The intensity of an AE will be assessed by the investigator as follows:

- Mild: Temporary event which is tolerated well by the patient and does not interfere with normal daily activities.
- Moderate: Event which results in discomfort for the patient and impairs his/her normal activity.

Severe: Event which results in substantial impairment of normal activities of patient.

#### Causal relation to trial medication/procedures

The assessment of the relationship of an adverse event to the administration of study drug is a clinical decision based on all available information at the time of the completion of the case report form. The investigator will evaluate the causal relationship of each adverse event with the administration of the investigational product(s) and/or trial procedures according to modified criteria of WHO 1991.

- Certain: A clinical event, including laboratory test abnormalities, occurring in a plausible time relationship to drug administration, and which cannot be explained by concurrent disease or other drugs or chemicals. The response to withdrawal of the drug (dechallenge) should be clinically plausible. The event must be definitive pharmacologically or phenomenologically, using a satisfactory rechallenge procedure if necessary.
- Probable: A clinical event, including laboratory test abnormality, with a reasonable time sequence to administration of the drug, unlikely to be attributed to concurrent disease or other drugs or chemicals, and which follows a clinically reasonable response on withdrawal (dechallenge). Rechallenge is not required to fulfill this definition.
- Possible: A clinical event, including laboratory test abnormality, with a reasonable time sequence to administrations of the drug, but which could also be explained by concurrent disease or other drugs or chemicals. Information on drug withdrawal may be lacking or unclear.
- Unlikely: A clinical event, including laboratory test abnormality, with a temporal relationship to drug administration which makes a causal relationship improbable, and in which other drugs, chemicals or underlying disease provide plausible explanations.
- Not related: A clinical event, including laboratory test abnormality, that does not follow a reasonable temporal sequence from trial participation and that is definitely caused by the patient's clinical state, other modes of therapy or other known etiology.

#### Outcome

The outcome of each AE must be assessed according to the following classification:

- completely recovered:	Patient has fully recovered with no observable residual effects				
- not yet completely recovered:	Improvement in the patient's condition has occurred, but the Patient still has some residual effects				
- deterioration:	Patient's overall condition has worsened				
- permanent damage:	AE has resulted in a permanent impairment				
- death:	Patient died due to the AE				
- ongoing:	AE has not resolved				
- unknown:	The outcome of the AE is not known because the patient did not return for follow-up (lost to follow-up)				

#### 6.2.2.3 Period of observation

In this trial, the period of observation for collection of adverse events extends from the time the patient has signed the informed consent document up to 14 days after the patient has routinely or prematurely terminated the study.

If the investigator detects a serious adverse event in a trial patient after the end of the period of observation, and considers the event possibly related to the prior trial, he should contact the sponsor to determine how the adverse event should be documented and reported.

## 6.2.2.4 Documentation of AEs and Follow up

At each visit after V0 the investigator must question the patient about the occurrence of any adverse event and note any abnormal laboratory findings. A neutral question such as "since the last visit have you felt any untoward or unusual symptoms other than those related to your illness?" elicits any adverse events experienced by the patient.

All AEs reported by the patient or detected by the investigator will be documented on the appropriate pages of the case report form (CRF). AEs must also be documented in the patient's medical records.

The following approach will be taken for documentation:

- All adverse events (whether serious or non-serious) must be documented on the "Adverse Event" page of the CRF.
- If the adverse event is serious (see Section 6.2.2.1), the investigator must complete, in addition to the "Adverse Event Page", a "Serious Adverse Event Form" at the time the serious adverse event is detected.

Every attempt should be made to describe the adverse event in terms of a diagnosis. If a clear diagnosis has been made, individual signs and symptoms will not be recorded unless they represent atypical or extreme manifestations of the diagnosis, in which case they should be reported as separate events. If a clear diagnosis cannot be established, each sign and symptom must be recorded individually.

All patients who have adverse events, whether considered associated with the use of the investigational products or not, must be monitored to determine the outcome. The clinical course of the adverse event will be followed up according to accepted standards of medical practice, even after the end of the period of observation, until a satisfactory explanation is found or the

investigator considers it medically justifiable to terminate follow-up, but no longer than 14 days after the end of the trial.

Should the adverse event result in death, a full pathologist's report should be supplied, if possible.

All questions on the completion and supply of adverse event report forms and any further forms issued to the investigator at a later date to clarify unresolved issues should be addressed to the sponsor.

